
Secondary Outcome Measure(s)
	
Key Secondary Efficacy Endpoints (Applicable for first placebo-controlled cycle only)
 
 1. The percentage of responders at maximum frown (as defined above) at week 12 (after the first treatment with BoNT/A-DP or placebo). 2. The percentage of responders at week 16 (after the first treatment). 3. The proportion of subjects with a ≥ 1 point reduction in FWS score at rest at week 4 in the first treatment cycle, based separately on the investigators'and the subjects'in-clinic assessments (applicable only for subjects who have a FWS score at rest ≥ 1 at baseline). 4. The percentage of responders at week 20 or later (after the first treatment). 5. The extent of change in psychological impact (emotional and social functioning and concerns relating to their glabellar lines) at week 4 after

the first treatment, in the BoNT/A-DP group in comparison with placebo, relative to baseline, as assessed by the modified Skindex-16 (Glabellar Line Quality of Life Scale, [GL-QoL]) and the FACE-Q(Appraisal of Lines Between Eyebrows and Age Appraisal visual analog [VAS] scales).

Additional Secondary Endpoints

6. The proportion of responders among BoNT/A-DP and placebo groups with a FWS score at maximum frown of 0 or 1 and an improvement ≥ 2 points in FWS score (at maximum frown) during the first treatment cycle visit relative to baseline, based on both the investigators' and the subjects' in-clinic assessments (composite endpoint, at weeks 1, 2 and 8).
7. The proportion of subjects with ≥ 2 -point reduction in FWS score (at maximum frown) in the BoNT/A-DP and placebo groups during the first treatment cycle visit relative to baseline, based on the independent rater's assessment of photographs (at baseline and visits 2, 4, 12, 16 and 20 weeks after treatment, within the first treatment cycle).
8. Time to onset of effect in the BoNT/A-DP and placebo groups in the first treatment cycle, as measured at weeks 1, 2 and 4 based separately on subject and investigator assessment. Onset of effect defined as at least a 1 point improvement in FWS score from baseline(at maximum frown). In addition, onset of effect will be assessed by subjects daily in the first 2 weeks after treatment, by recordings in the subject diary.

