9. The extent of subject perceptions of effect of, and satisfaction with, treatment in the BoNT/A-DP and placebo groups, during each treatment cycle, as assessed by the FACE-Q Satisfaction with Outcome Scale.
10. The proportion of subjects with a > 1 point reduction in FWS score at rest in the BoNT/A-DP and placebo groups, relative to baseline, during the first treatment cycle, based on the independent rater's assessment of photos.
11. The percentage of subjects with a FWS score of 0 or 1 and an improvement ≥ 2 points in FWS score at maximum frown (investigator and subject assessment) at 4 weeks after re-treatment relative to the rating at the preceding end of cycle visit.

Secondary Safety Endpoints

1. Frequency, severity and causal relationship of adverse events (AEs), serious adverse events (SAEs) and adverse events of special interest (AESIs) during the entire study period.
2. Antibody formation, evaluation pre-dose before each treatment, at 4 weeks after each treatment and at the final study visit.

	3. Safety assessments by evaluating hematology, clinical chemistry, vital signs and electrocardiogram (ECG) as per study schedule (Section 2.1).
INVESTIGATIONAL MEDICINAL PRODUCT(S), DOSE AND MODE OF ADMINISTRATION	
Active	
BoNT/A-DP
 
Dosage form: Injection, lyophilizate for solution for injection
 
Dosage frequency: 20 U/treatment comprising a total of five intramuscular (i.m.) injections of BoNT/A-DP (4 U per 0.1 mL injection) administered at a minimum interval of 12 weeks.
 
Mode of administration: Two sites in each corrugator superciliaris muscle and one site in the procerus muscle, with an injection volume of 0.1 mL into each site.

Placebo	
Sterile, 0.9% Sodium chloride injection
 
Dosage form: Injection
 
Dosage frequency: A single treatment comprising five injections of 0.1 mL each.
 
Mode of administration: Same as for Study IMP. Two sites in each corrugator superciliaris muscle and one site in the procerus muscle, with an injection volume of 0.1 mL into each site.

SUBJECT SELECTION	
Targeted Accrual	
700 subjects. Subject accrual planned as follows:
 
 • Approximately 50% of subjects enrolled in EU and 50% in US. • Approximately 18 sites planned, hence for a 3:1 (BoNT/A-DP:Placebo) randomization scheme, each site should target randomizing at least 32-40 subjects.

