6.4.2.2 Additional Secondary Endpoints

6. The proportion of responders among BoNT/A-DP and placebo groups with a FWS score of 0 or 1 and an improvement ≥ 2 points in FWS score (at maximum frown) during the first treatment cycle visit relative to baseline, based on both the investigator's and the subject's in-clinic assessments (composite endpoint, at weeks 1, 2 and 8).
7. The proportion of subjects with ≥ 2 point reduction in FWS score (at maximum frown) in the BoNT/A-DP and placebo groups during the first treatment cycle visit relative to baseline, based on the independent rater's assessment of

- photographs (at baseline and visits 2, 4, 12, 16 and 20 weeks after treatment, within the first treatment cycle).
8. Time to onset of effect in the BoNT/A-DP and placebo groups in the first treatment cycle, as measured at weeks 1, 2 and 4 based separately on subject and investigator assessments. Onset of effect defined as at least a 1 point improvement in FWS score from baseline (at maximum frown). In addition, onset of effect will be assessed by subjects daily in the first 2 weeks after treatment, by recordings in the subject diary.
 9. The extent of subject perceptions of effect of, and satisfaction with, treatment, in the BoNT/A-DP and placebo groups, during each treatment cycle, as assessed by the FACE-Q Satisfaction with Outcome Scale.
 10. The proportion of subjects with a ≥ 1 point reduction in FWS score at rest in the BoNT/A-DP and placebo groups, relative to baseline, during the first treatment cycle, based on the independent rater's assessment of photos.
 11. The percentage of subjects with a FWS score of 0 or 1 and an improvement of ≥ 2 points in FWS score at maximum frown (investigator and subject assessment) at 4 weeks after re-treatment relative to the rating at the preceding end of cycle visit.

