The analysis using the investigator's in-clinic assessment will be conducted first with respect to the hierarchical order of key secondary endpoints, with the analysis using the subjects's in-clinic assessment second.

The analysis on the investigator's in-clinic assessment will be conducted only for subjects who have an investigator's in-clinic assessment of a FWS score at rest > 1 at baseline. This will similarly be applied for the analysis of the subject's in-clinic assessment.

Subjects with missing investigator in-clinic assessments at baseline or week 4 visit will be assigned as being non-responders for this endpoint. This will similarly be applied for the subject's in-clinic assessment.

Analysis of key secondary endpoint 4: The percentage of responders at week 20 or later (after the first treatment).

The analysis of visit week 20 will be conducted on observed values only, i.e. missing investigator or the subject in-clinic assessments on FWS at baseline or visit week 20 will be excluded from the analysis but not assigned as being non-responders. Subjects who were re-treated before visit week 20 are considered to be non-responders.

In addition, the same analyses, inclusive the additional exploratory analyses as described for the primary endpoint, will be conducted (for subgroups also).

Analyses of other visits after first treatment but before re-treatment are exploratory only. Additional exploratory analyses, as described for the primary endpoint, will not be conducted, with the exception of the calculation of 95% CIs.

Analysis of key secondary endpoint 5: The extent of change in psychological impact (emotional and social functioning, and concerns relating to glabellar lines) at week 4 after the first treatment, in the BoNT/A-DP group in comparison with placebo, relative to baseline, as assessed by the modified Skindex-16 (GL-QoL) and the FACE-Q Appraisal of Lines Between Eyebrows and FACE-Q Age Appraisal VAS.

The modified Skindex-16 (GL-QoL) and FACE-Q Appraisal of Lines Between Eyebrows scale and FACE-Q Age Appraisal VAS scales will be analyzed according to the foreseen analysis approach of these tools, as described below.

Emotional and Social Functioning

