4.2 Key Secondary efficacy endpoints

The key secondary efficacy endpoints of this study are:

1. The percentage of responders at maximum frown at week 12 (after the first treatment with BoNT/A-DP or placebo).
2. The percentage of responders at week 16 (after the first treatment).
3. The proportion of subjects with a ≥ 1 point reduction in FWS score at rest at week 4 in the first treatment cycle, based separately on the investigators' and the subjects' in-clinic assessments (applicable only for subjects who have a FWS score at rest ≥ 1 at baseline).
4. The percentage of responders at week 20 or later (after the first treatment).
5. The extent of change in psychological impact (emotional and social functioning and concerns relating to their glabellar lines) at week 4 after the first treatment, in the BoNT/A-DP group in comparison with placebo, relative to baseline, as assessed by the modified Skindex-16 (Glabellar Line Quality of Life Scale [GL-QoL]) and the FACE-Q (Appraisal of Lines Between Eyebrows and Age Appraisal visual analog scales (VAS)), respectively.

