8.6.3 Analysis of secondary efficacy endpoint(s)

The following order of tests will be defined for the analysis of the key secondary endpoints:

- Primary endpoint (composite endpoint)
- Key secondary endpoint 1 (composite endpoint)
- Key secondary endpoint 2 (composite endpoint)
- Key secondary endpoint 3
 - 3.1: The investigator's in-clinic assessments
 - 3.2: The subject's in-clinic assessments
- Key secondary endpoint 4 (composite endpoint)

Statistical Analysis Plan (SAP)

- Key secondary endpoint 5
 - 5.1: The modified Skindex-16 (GL-QoL) Emotional domain
 - 5.2: The modified Skindex-16 (GL-QoL) Functioning domain
 - 5.3: The modified Skindex-16 (GL-QoL) Overall score
 - 5.4: The FACE-Q Appraisal of Lines Between Eyebrows scale
 - 5.5: The FACE-Q Age Appraisal VAS score

For key secondary endpoints 2 – 4, the p-value to be considered within the hierarchical testing procedure is the one resulting from the Cochran-Mantel-Haenszel test as described for the primary efficacy endpoint in the first paragraph entitled “Primary Analysis” of section 8.6.2.

Analysis of key secondary endpoint 1: The percentage of responders at maximum frown (as defined above for the primary efficacy endpoint) at week 12 (after the first treatment with BoNT/A-DP or placebo).

The same analyses, inclusive the additional exploratory analyses, as described for the primary endpoint will be conducted.

Analysis of key secondary endpoint 2: The percentage of responders at maximum frown (as defined above for the primary efficacy endpoint) at week 16 (after the first treatment).

The analysis of the week 16 visit will be conducted on observed values only, i.e. missing investigator or the subject in-clinic assessments with the FWS at baseline or week 16 visit will be excluded from analysis but not assigned as being non-responders. Subjects who were re-treated before visit week 16 are considered to be non-responders.

In addition, the same analyses, inclusive the additional exploratory analyses, as described for the primary endpoint will be conducted as exploratory analyses. Subjects who were re-treated before visit week 16 are considered to be non-responders in all these analyses.

Analysis of key secondary endpoint 3: The proportion of subjects with a > 1 point reduction in FWS score at rest at week 4 in the first treatment cycle, based separately on the investigator and the subject in-clinic assessments

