8.6.4 Additional secondary analyses

The additional secondary efficacy endpoints will be analyzed applying the appropriate statistical method for the comparison of both treatment arms. For proportions

- of responders with a FWS score of 0 or 1 and an improvement ≥ 2 points in FWS score at maximum frown,
- of subjects with ≥ 2 point reduction in FWS at maximum frown,
- of subjects with a ≥ 1 point reduction in FWS at rest, and
- of subjects with an improvement of ≥ 2 points in FWS at maximum frown at 4 weeks after re-treatment,

the Cochran-Mantel-Haenszel test (with stratification variable site) and the Pearson χ^2 -test will be applied. In case of a total number of observations below 30, or in case of at least one cell frequency below 5, Fisher's exact test will be used instead of the χ^2 -test. Two-sided 95% CIs for response rates will be calculated, where appropriate. Additionally the cumulative proportions of effects at weeks 1, 2, and 4 will be calculated. Time to onset of effect in the first treatment cycle will be analyzed descriptively and by using the Kaplan-Meier method. Moreover, the daily assessments of the line severity when frowning will be analyzed descriptively. The FACE-Q satisfaction with outcome scale will be analyzed descriptively.

All endpoints, with exception of “responder” 4 weeks after re-treatment, will be analyzed for the first treatment cycle only. The analysis of “responder” 4 weeks after re-treatment will be conducted on observed values only, i.e. subjects with missing investigator or the subject in-clinic assessments on FWS week 4 or at the preceding end of the cycle visit will be excluded from analysis. Subjects who were treated with placebo during the first treatment cycle are excluded from the analysis of this endpoint, but not assigned as being non-responders. A two-sided McNemar test (using a significance level of 0.05) will be used to compare the response proportions between week 4 re-treatment visit and at the preceding end of the cycle visit. This endpoint will be separately analyzed for each open label extension cycle.

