9 CHANGES TO PLANNED ANALYSIS FROM STUDY PROTOCOL

The following changes to the planned analysis from the study protocol are designated:

- The definition of the SAF in section 6 was changed compared to the definition in section 12.2 of the study protocol in order to include all treated subjects in the safety analyses.
- The analysis of antibody formation described in section 8.7.3 was changed compared to the description in the study protocol.

Statistical Analysis Plan (SAP)

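### Key secondary endpoint 3 is defined with ≥1 for both the fall and the baseline score but analysed with >1 for both, so the confirmatory tests at steps 3.1 and 3.2 are not uniquely specified

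*SAP*

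**What the plan says.** The endpoint definition is the same in the Protocol synopsis, Protocol 6.4.2.1 and SAP 4.2. The response is "The proportion of subjects with a ≥ 1 point reduction in FWS score at rest at week 4 in the first treatment cycle", assessed separately by investigator and subject, and the endpoint is "applicable only for subjects who have a FWS score at rest ≥ 1 at baseline".

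The analysis text differs. SAP 8.6.3 introduces the analysis as "The proportion of subjects with a > 1 point reduction in FWS score at rest at week 4 in the first treatment cycle", and Protocol 12.4.2 has the same words. Both sections then restrict the analysis to subjects with an "assessment of a FWS score at rest > 1 at baseline", first for the investigator's rating and likewise for the subject's. SAP 8.6.3 extends that restriction to every analysis of this endpoint, including the exploratory ones.

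The endpoint is confirmatory. SAP 8.6.1.1 places it at steps 3.1 (investigator) and 3.2 (subject) of a fixed sequence at one-sided 0.025. SAP 8.6.3 takes the Cochran-Mantel-Haenszel (CMH) p-value into that sequence.

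No section says which wording prevails. SAP section 9, under "The following changes to the planned analysis from the study protocol are designated", lists two items (the safety set and the antibody analysis) and neither concerns this endpoint.

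**The concern.** A fixed sequence protects the type I error only if each hypothesis is settled in advance. Here two readings of steps 3.1 and 3.2 remain open, and they differ in who is analysed as well as in what counts as response. A programmer working from the methods section would test one hypothesis; a programmer working from the endpoint section would test another.

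The consequence goes beyond endpoint 3. If 3.1 or 3.2 fails, everything after it becomes exploratory: any untested part of endpoint 3, the week 20 responder endpoint (key secondary 4), and the five quality-of-life and FACE-Q tests (5.1 to 5.5). If the choice is made after unblinding, or looks as if it was, all of these claims can be challenged.

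**Working it through.** **What the two wordings count.** The FWS takes the values 0, 1, 2 and 3. A fall of more than 1 point is therefore a fall of at least 2, and a baseline above 1 means 2 or 3.

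| Change, baseline to week 4 | Definition (≥1 fall, baseline ≥1) | Analysis text (>1 fall, baseline >1) |
|---|---|---|
| 1→0 | responder | not analysed |
| 2→1 | responder | non-responder |
| 2→0 | responder | responder |
| 3→2 | responder | non-responder |
| 3→1 | responder | responder |
| 3→0 | responder | responder |

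Six response changes become three, and all baseline-1 subjects leave the denominator.

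**Which wording was probably meant.** Additional secondary endpoint 10, also at rest, shows the same split. The synopsis has "The proportion of subjects with a > 1 point reduction in FWS score at rest in the BoNT/A-DP and placebo groups", while Protocol 6.4.2.2 and SAP 4.3 have "The proportion of subjects with a ≥ 1 point reduction in FWS score at rest in the BoNT/A-DP and placebo groups". SAP 8.6.4 lists the at-rest proportion as "of subjects with a ≥ 1 point reduction in FWS at rest". With three consistent definitions of endpoint 3 and no declared change, this points to ≥1.

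**The plan's own figures.** The documents give no sample size, power or response rate for endpoint 3. The primary-endpoint figures reproduce: the exact one-sided Fisher test at 0.025 with 60% vs 10% has 91.6% power at 42+14 (89.3% at 39+13), and the 95% CI half-width is 1.96 × √(0.6 × 0.4 / 450) = 4.5%. Neither depends on endpoint 3.

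**Illustration of power.** All at-rest inputs below are assumptions. Eligible numbers are the planned 525+175 times the eligible share.

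| Assumed baseline rest score 0/1/2/3 | Share ≥1 | Active+placebo, ≥1 | Share >1 | Active+placebo, >1 |
|---|---|---|---|---|
| A: 20/40/30/10% | 80% | 420+140 | 40% | 210+70 |
| B: 40/40/15/5% | 60% | 315+105 | 20% | 105+35 |
| C: 10/30/40/20% | 90% | 472+158 | 60% | 315+105 |

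The test is z = (p₁ − p₂) / √[p(1 − p)(1/n₁ + 1/n₂)], with p the pooled rate, rejecting at z ≥ 1.96. Power is the exact sum of binomial probabilities over all rejecting outcomes.

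| Rule | Assumed response, active vs placebo | A | B | C |
|---|---|---|---|---|
| ≥1 | 30% vs 15% | 96% | 89% | 98% |
| >1 | 5% vs 2% | 10% | 1% | 20% |
| >1 | 10% vs 3% | 48% | 18% | 68% |
| >1 | 20% vs 2% | over 99% | 87% | over 99% |

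The rules can also be linked by assuming that a fixed share of all falls is 2 points or more among baselines 2 and 3 (mix A):

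| Any fall, active vs placebo | ≥1 rule | >1 rule, 10% share | >1 rule, 50% share |
|---|---|---|---|
| 30% vs 15% | 96% | 1% | 36% |
| 50% vs 15% | over 99% | 14% | 94% |

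For example, 30% vs 15% at a 50% share becomes 15% vs 7.5% on 210+70 subjects.

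**Check against the planned test.** Simulating the site-stratified CMH test with 18 equal sites, and pooling sites with fewer than 3 placebo subjects, gives powers within about 2 percentage points of these. In mix B under >1 there are only about 35/18 ≈ 2 placebo subjects per site, so nearly all sites pool and the agreement there is largely automatic. If eligible counts vary at random between sites, mix B at 20% vs 2% falls from 87% to 82%.

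**A separate, minor point.** SAP 8.6.3 omits the LOCF analysis for this endpoint on the ground that it must equal the non-responder analysis. That does not follow. Protocol 10.1.1 has rest scores taken at weeks 1 and 2 as well, so a subject improved at week 2 and missing at week 4 is a responder under LOCF and a non-responder under the main rule. This affects an exploratory table only.

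**The case against.** The strongest reply is that the conflict lies in a printed sign and not in the plan. A ≥ can lose its underline when a PDF is read, and endpoint 10 shows the same slip. None of the four disputed statements contains a ≥ that would show the sign was read correctly there. This is possible but unproven. The strict sign stands in both documents, at both the response threshold and the eligibility rule, while ≥ survives in neighbouring sections. It does mean that checking the source files comes first.

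A second reply is that intent can be recovered: three definitions agree, and the >1 fall appears in a sentence that only restates the endpoint. That narrows the doubt without removing it, because the baseline restriction is an operative instruction. The table templates might settle the matter, but they are in a separate document that is not available here.

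Third, the power figures do not establish harm. This is right. A range from 1% to over 99% reflects the assumed inputs, and the low values need small effects or few two-point falls. The case rests on six versus three response changes and on the confirmatory role of the endpoint. It is also true that type I error is controlled once one wording is fixed in advance.

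**Conclusion.** The concern holds. As written, the defined endpoint and the analysed endpoint are different hypotheses at two confirmatory steps, and nothing in either document ranks one over the other. The certain part is the count: half of the six response changes and all baseline-1 subjects are in dispute. The loss of power under the >1 reading cannot be fixed from the documents and runs from negligible to severe, depending on the assumed rest-score mix and the share of two-point falls. In the linked scenarios it is lower by construction, since both the numbers and the rates fall. That ≥1 was intended is well supported but is an inference; whether the > is a slip or a reading artefact is open until the source is checked. The matter should be settled before unblinding.

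**What to change.** Before unblinding:

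1. Check the source files of both documents for the sign at each place named above.
2. If the strict sign is really there, change the fall and the baseline restriction in SAP 8.6.3 and Protocol 12.4.2 to ≥1, to match the synopsis, Protocol 6.4.2.1 and SAP 4.2.
3. Change endpoint 10 in the Protocol synopsis to ≥1, to match Protocol 6.4.2.2 and SAP 4.3.
4. Minor: delete the SAP 8.6.3 statement that LOCF must give the same result, and run LOCF for this endpoint as an exploratory table.

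The cost is wording plus one table. A revision of the protocol may need ethics and regulatory approval if it is judged substantial (Protocol 15.2). A lighter route to the same result is to correct SAP 8.6.3 and record the departure from Protocol 12.4.2 in SAP section 9.
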